#### **6.4 Visit C: Week 1 (Target Quit Day) (Approximately 45 minutes in person)**

At the in-person visit, we will measure breath CO level and the participant will receive a four-week supply of study medication. The nurse or coordinator (trained and supervised by the nurse or physician) will review with the participant instructions for taking the study medication and record any AEs that the participant may have experienced. The nurse or coordinator will also collect empty medication blister packs and any unused medication. In-person or by telephone, participants will complete the PHQ-9, QSU, will be interviewed with the TLFB, and will receive a 20-minute, “quit-day” counseling session to review the initial quit attempt, identify potential reasons for relapse, and review a plan to avoid tempting situations.

#### **6.5 Visit D: Week 3 (Approximately 25 minutes by telephone or in person)**

Participants will be asked to complete the PHQ-9 and the TLFB by telephone. They will then receive a 10-minute booster counseling session that focuses on reinforcing success and reviewing the quit plan (for participants who have quit smoking) or re-establishing a quit date

CONFIDENTIAL

and restarting the cessation process (for participants who have relapsed to smoking). The counseling schedule reflects the changing needs of the pregnant smoker during the course of pregnancy and smoking cessation (155), with more intensive help offered in the earliest phase of treatment and continued efforts to prevent relapse in the later stages.

#### **6.6 Visit E: Week 5. (Approximately 30 minutes in-person)**

At the in-person visit, we will measure breath CO level, and participants will meet with a study nurse or coordinator working under the supervision of the nurse or physician to receive a five-week supply of study medication. The nurse or coordinator will review with the participant instructions for taking the study medication and record any AEs that the participant may have experienced. The nurse or coordinator will also collect empty medication blister packs and any unused medication. Two tubes of blood (14 cc) will be drawn at this visit for shipment to [name] laboratory at the University of Toronto to measure plasma concentrations of bupropion and hydroxybupropion. Participants will be asked to complete PHQ-9, QSU, and TLFB, either in person or by telephone. They will then receive a 10-minute booster counseling that focuses on reinforcing success and reviewing the quit plan (for participants who have quit smoking) or re-establishing a quit date and restarting the cessation process (for participants who have relapsed to smoking). Suicidal risk will be assessed using the MINI Suicidality section (B).

#### **6.7 Visit F: Week 7. (Approximately 15 minutes by telephone or in person)**

Participants will be asked to complete the PHQ-9 and TLFB by telephone.

#### **6.8 Visit G: Week 10 (Endpoint). (Approximately 25 minutes in-person)**

At the in-person visit, we will measure breath CO level. The nurse or coordinator (trained and supervised by the nurse or physician) will review with the participant any AEs that the participant may have experienced. The nurse or coordinator will also collect empty medication blister packs and any unused medication. Participants will be asked to complete the PHQ-9, QSU, MED-Q, and TLFB in-person. Suicidal risk will be assessed using the MINI Suicidality section (B).

#### **6.9 Visit H: Week 24 Post-TQD Follow-up Visit (Approximately 20 minutes in-person)**

At the in-person visit, we will measure breath CO level and participants will be asked to complete the PHQ-9 and TLFB. Visit may be completed at same time as inpatient hospital visit or the outpatient postpartum visit.

#### **6.10 Visits I & J: Postpartum Week 2 and Postpartum Week 6 Visits (Approximately 25 minutes by telephone or in person)**

At each visit, participants will be asked to complete the PHQ-9 and TLFB by telephone. They will then receive a 10-minute booster counseling session. The session will focus on reinforcing success and reviewing the quit plan (for participants who have quit smoking) or re-establishing a quit date and restarting the cessation process (for participants who have relapsed to smoking). Women who have failed to stop smoking or have relapsed will be referred for counseling by staff at the obstetrics clinic from which they were recruited and at which they will be receiving early postnatal care.

CONFIDENTIAL

### **6.11 Early Termination Visit (Approximately 30 minutes, in-person or divided between in-person and telephone sessions)**

Participants who discontinue treatment prematurely will be asked to complete an end-of-treatment evaluation and all scheduled assessments to facilitate intention-to-treat (ITT) analyses. Participants will be informed of these procedures prior to study enrollment. Participants who terminate participation in the treatment prior to Week 10 will also be asked to complete the scheduled end-of-treatment (Week 10) procedures. For this and any other visit that cannot be completed in-person, assessments will be conducted by telephone.

### **6.12 Other Study Procedures and Considerations**

Screening and baseline visits cannot occur on the same day. The maximum time permitted to elapse between completion of the screening visit and completion of the baseline visit is 30 days. Every effort will be made to complete visits within a 3-day window before or after the date scheduled for the visit as shown in Table 2. However, because the analysis will be intent-to-treat, we will reasonably accommodate subjects' time constraints by extending the window as needed to complete all study visits. During the week prior to each of the visits (B through J), a reminder call will be made to the participant concerning the next scheduled visit. At the reminder call for Visit H (24 weeks post-TQD) the participant will be asked whether she had smoked at all during the previous week. Visit H will be held plus or minus 28 days from the scheduled 24 week post-TQD. This large window accommodates changes in delivery dates and also allows the visit to coincide with the inpatient delivery or the 6-week post-partum office visit, an important convenience for a new mother. If she acknowledges having smoked, an in-person visit is not required but may be held. If she reports no smoking, an in-person visit will be conducted to verify self-report using breath CO measurement. Because breath CO is a non-invasive and simple test, as well as an important outcome measure, we will collect a breath CO reading at all in-person opportunities when feasible, including at time of delivery and at the time of the 6-week post-partum visit. If the blood draw is unsuccessful at the baseline visit, a second attempt will be made at the Week 5 visit. If the second draw is successful, the baseline tubes will also be drawn (for all baseline tests if the participant is still smoking or for DNA only if the participant is no longer smoking). If the second draw is not successful, we will collect DNA from the patient's saliva using the Oragene Discover Kit (PD-LB-00191).

Monthly protocol adherence meetings will be conducted with the coordinators at each site to ensure adherence to the counseling protocol. All sessions, with permission from the participant, will be audiotaped and 15% will be randomly selected for evaluation by [name] using fidelity forms to determine adherence to the elements of the counseling, record the duration of the session, assess the therapeutic relationship and the coordinators' attention to the participants' condition, and provide individual feedback and re-training to the coordinators, as needed. One session from each participant will be selected from among the initial, quit day, or booster sessions for review. The standardized checklists will yield a protocol adherence score (from 1 = "not at all" to 7 = "extensively") and inter-rater reliability will be computed following the model of Shrout and Fleiss (156). This process is modeled on previous cessation clinical trials in pregnant smokers (157) and the general population of smokers (158), which yielded intraclass correlation coefficients of 0.87-0.99. Audio recording is not a requirement of the study and participants will be given the opportunity to opt out. Following evaluation, the recordings will be deleted electronically.

Throughout the study, if a participant misses a study visit due to a vacation or an unforeseen event, study personnel will reschedule the study visit for as soon thereafter as possible. Study staff will mail the study medication to the participant via secure mail or courier under the

CONFIDENTIAL

supervision of a study nurse or doctor. Participants will only be provided with enough study medication to allow them to maintain their daily dosage of study medication until their next scheduled visit. An investigator will determine how many additional weeks of study medication a participant will be allowed to receive without attending a study visit. In extenuating circumstances, a home visit may be necessary. In those cases, study staff will utilize public transportation (SEPTA), a rental car, or taxi for transportation to and from the visit at the subject's home.

The nurse or coordinator (trained and supervised by the nurse or physician) will provide instructions over the phone on how to take the study medication as per the dosing schedule and record any adverse events that have occurred since the last study visit. Study nurses or coordinators will instruct participants to call our study staff at any time to discuss any problems or concerns they may have while taking the study medication. All participants will be provided phone numbers to contact the study staff during office hours and the pager number for off-hours contact 24 hours a day. Participants will be asked to come in for their next study visit as soon as possible.

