## **4. Participant Selection and Withdrawal**

### **4.1. Inclusion Criteria**

1. Currently smoking on average 3 or more cigarettes per day for the preceding 7 days with a breath CO of at least 5 ppm and wants to quit smoking
2. Pregnant at 13-26 weeks gestation (to maximize safety and the likelihood of receiving 10 weeks of treatment)
3.  $\geq 18$  years of age
4. Able to speak and read English at a 6th grade level or higher, using the Slosson Oral Reading Test (SORT)
5. Committed to remaining in the geographic area for at least 3 months postpartum
6. Able to sign written informed consent and commit to completing the procedures involved in the study.
7. Methadone or buprenorphine-maintained women must be in methadone or buprenorphine treatment for a minimum of 2 weeks prior to entering the study. Their 2 most recent urine drug screens, consecutive and administered at least one week apart, must both be positive for methadone or buprenorphine and negative for drugs of abuse other than cannabis. Participants who screen positive for other drugs at either time point will not be enrolled in the study until they meet this criterion.

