### **4.3. Participant Recruitment and Screening**

All sites will have a senior clinician to oversee the integration of the trial into clinical practice. Approval from the City of Philadelphia Institutional Review Board and the Health Commissioner's Office will be obtained given the involvement of Philadelphia Department of Public Health data, staff, and clients at the Jefferson MATER site, where methadone-maintained pregnant smokers will be enrolled. Buprenorphine-treated subjects will be recruited from the "Mothers MATTER" program at the Dickens clinic and from the Jefferson MATER site. As in our previous successful clinical trials (e.g., 14, 47, 52), we will use experienced and trained research staff to identify and screen potentially eligible participants in the clinics. Recruitment sites will also be provided with IRB-approved materials designed to raise awareness of the study, including posters and brochures to be displayed prominently in all clinic areas. We will also encourage referrals from clinicians in the surrounding areas at each site, and will recruit through newspapers, maternity magazines and social media. Interested and potentially eligible participants will be scheduled for an intake session (week -1) to determine eligibility. For details on Screening, see 6.2 Informed Consent and Screening Visit below.

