The initial assessment in the clinic will help to exclude ineligible participants, facilitate clearance by an obstetrician for any medical condition that requires approval (e.g., mild hypertension), and ensure that the woman's gestational age is 13-26 weeks. Gestational age will be assessed for enrollment purposes based on the method used by the NICHD-sponsored Maternal-Fetal Medicine Units Network. The gestational age will be based on the projected estimated date of delivery (EDD), as determined by U/S and the last menstrual period (LMP; see below). Because the project EDD depends on information from the earliest dating U/S, if no U/S has been performed previously, one will be performed to determine eligibility. The EDD also requires that the first day of the LMP be determined and a judgment made as to whether or not the participant has a "sure" LMP.

- If the LMP date is uncertain, the U/S measurements obtained at the participant's first U/S will be used to determine the projected gestational age, by the standard method used at the recruitment site.
- If the date of the LMP is certain and the U/S confirms the gestational age within +/- 7 days, the LMP-derived gestational age will be used to determine the project gestational age.
- If the U/S-determined gestational age does not confirm the LMP-generated gestational age within +/- 7 days, the U/S will be used to generate the project gestational age.

Thus, all participants will be assigned a project EDD and gestational age when they are evaluated for enrollment. An U/S machine is available at each recruitment site and results will be supervised and reviewed by [name] (Penn) or [name], M.D. (Jeff).

CONFIDENTIAL

**6.3 Visit B: Baseline (Pre-quit) (Approximately 90 minutes, in-person or divided between in-person and telephone sessions)**

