Although this session requires an in-person visit, part of the session may be completed via telephone. The session must be completed 1-30 days after completion of the screening visit. At the in-person visit, we will measure breath CO level and draw three tubes (i.e., 21 cc) of maternal blood to assess NMR and provide DNA for genotyping. Blood will be stored in a coded manner in a designated -80° freezer and shipped on dry ice to the laboratory of [name] at the University of Toronto approximately every four months throughout the study. Samples from both sites will be shipped from their storage location at Penn (see section 9.5) and will follow the guidelines for shipping international biological samples as required by the university.

Table 2: Study Assessments

	Visit A	Visit B	Visit C	Visit D	Visit E	Visit F	Visit G	Visit H	Visit I	Visit J
	Screen	Baseline (Pre-quit)	Wk 1 (TQD)	Wk 3	Wk 5	Wk 7	Wk 10	Wk 24	Wk 2 PP	Wk 6 PP
ICF with HIPAA	X									
Medical record review	C									
Med History Questionnaire	X									
Demographics	X									
SORT	X									
MINI 	X				X 		X 			
TLFB (preceding 30 days)	X									
Gestational Age	X, C									
Blood sample: DNA, NMR		X								
Breath CO*	X	X	X		X		X	X 		
Dispense medication		X	X		X					
Text messaging		Daily	Daily	Daily	Daily	Daily	Daily			
Assessment of AEs and medication adherence		X	X	T	X	T	X			
Weight, blood pressure	X or C	C	C	C	C	C	C			
Pulse		X	X		X		X			
ACE questionnaire		X or T								
Smoking History Questionnaire		X or T								
FTND		X or T								
BISS		X or T								
WEAQ		X or T								
PHQ-9	X	X or T	X	T	X	T	X	X	T	T
QSU		X or T	X		X		X			
MED-Q							X			
TLFB (since last visit)		X or T	X	T	X	T	X	X	T	T

CONFIDENTIAL

This material is the property of the University of Pennsylvania. Do not disclose or use except as authorized in writing by the study sponsor

Smoking cessation counseling (30 min)		X							
Smoking cessation counseling (20 min)			X						
Smoking cessation counseling (10 min)				T	X			T	T
Blood sample: [bupropion, hydroxybupropion]					X				
Birth outcome data								C	

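### Gestational age is checked at screening, but Visit B may follow 30 days later with no rule that the 13-26 week limit still holds, so treatment can start at about 30-31 weeks

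*Combined protocol and SAP*

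**What the plan says.** Section 4.1 sets the gestational criterion and gives its reason: "Pregnant at 13-26 weeks gestation (to maximize safety and the likelihood of receiving 10 weeks of treatment". The smoking criterion in the same list reads: "Currently smoking on average 3 or more cigarettes per day for the preceding 7 days with a breath CO of at least 5 ppm". Neither names a visit, and the upper limit is not defined in days.

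Other sections place the eligibility decision at screening. Section 4.3 has women "scheduled for an intake session (week -1) to determine eligibility". Section 6.2 (Visit A) says the initial assessment will "ensure that the woman's gestational age is 13-26 weeks", and adds: "all participants will be assigned a project EDD and gestational age when they are evaluated for enrollment". Table 2 marks gestational age at Visit A only.

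The gap to Visit B is stated twice. Section 6.3 says of the baseline session: "The session must be completed 1-30 days after completion of the screening visit". Section 6.12 says: "The maximum time permitted to elapse between completion of the screening visit and completion of the baseline visit is 30 days".

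Treatment begins after Visit B (section 5.2), with the first dose the following morning (section 6.3). The randomisation steps in section 5.3 include no confirmation of eligibility. Table 2 schedules breath CO and a Timeline Follow-back (TLFB) since the last visit at Visit B, but no section says what follows if the woman no longer meets the smoking criterion.

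**The concern.** The limit is justified by safety and by the chance of completing 10 weeks of treatment. Both concern the time when drug is taken, yet the limit is checked up to a month earlier. If the full gap is used, the explicit 30-day rule undercuts the limit's own rationale.

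The consequence reaches the primary endpoint. Some late starters may deliver before finishing treatment or before Visit G (week 10). Section 6.11 lets a missed visit be done by telephone, but section 3.2 counts a woman without a breath sample as smoking. Non-attendance around delivery would then enter the week-10 outcome as treatment failure.

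The smoking criterion has a weaker form of the same gap. A woman who stops smoking between screening and Visit B can be randomised. If she stays abstinent she counts as a success in whichever arm she joins, which dilutes the treatment effect.

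**Working it through.** **Inputs from the protocol.** Upper limit 26 weeks (4.1), read as 26w0d (day 182) or 26w6d (day 188); maximum gap 30 days (6.3, 6.12); first dose one day after Visit B (6.3); 10 weeks, i.e. 70 dosing days, so the last is first dose + 69; 180 women per arm (5.3); week-10 quit rates 21.2% and 35.9%, two-sided alpha 0.05, stated power 88% (7.1, 7.1.1). The protocol does not date randomisation expressly. I place it at Visit B, where drug is first dispensed; the dosing dates do not depend on this.

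**Calendar arithmetic**

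| | Limit = 26w0d | Limit = 26w6d |
|---|---|---|
| Visit B at +30 days | 182 + 30 = 212 = 30w2d | 188 + 30 = 218 = 31w1d |
| First dose, +1 | 213 = 30w3d | 219 = 31w2d |
| Last dosing day, +69 | 282 = 40w2d | 288 = 41w1d |
| Last dosing day if the limit held at Visit B | 182 + 1 + 69 = 252 = 36w0d | 188 + 1 + 69 = 258 = 36w6d |

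If the limit held at Visit B, every 10-week course would end before 37 weeks, the protocol's own preterm threshold (3.2).

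**Illustrative share of women affected.** The documents give no distribution of gestational age or of gap. Assume screening age uniform over 13w0d-26w6d (days 91-188, 98 values). The last dosing day is screening day + gap + 70. It falls at 37w0d (day 259) or later when screening day + gap is at least 189. For a gap of g days, exactly g of the 98 screening days qualify.

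- Gap uniform over 1-30 days: (1 + 2 + ... + 30) / (98 × 30) = 465 / 2,940 = 15.8%, or about 57 of 360.
- Fixed 7-day gap (the nominal week -1 of section 4.3): 7 / 98 = 7.1%, or about 26 of 360.

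If the limit means 26w0d (92 screening days), fewer courses reach 37w0d. For gaps of 7 days or more, g − 6 screening days qualify, giving 300 / 2,760 = 10.9% and 1 / 92 = 1.1% respectively.

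**Power, starting from the plan's figure.** Two-proportion z-test, 180 per arm:

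- Difference 0.147; pooled rate 0.2855.
- Null SE = √(2 × 0.2855 × 0.7145 / 180) = 0.0476.
- Alternative SE = √((0.212 × 0.788 + 0.359 × 0.641) / 180) = 0.0470.
- Power = Φ((0.147 − 1.96 × 0.0476) / 0.0470) = 87.3%, which reproduces the stated 88% to within a point.

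Now let a fraction q of each arm have quit before randomisation, and a fraction r of those be abstinent at week 10 regardless of arm. Each rate becomes p′ = (1 − q)p + qr. Both q and r are assumptions.

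| q | r | Placebo | Bupropion | Power |
|---|---|---|---|---|
| 3% | 50% | 22.1% | 36.3% | 84.8% |
| 3% | 100% | 23.6% | 37.8% | 83.8% |
| 5% | 50% | 22.6% | 36.6% | 83.0% |
| 5% | 100% | 25.1% | 39.1% | 81.3% |
| 10% | 50% | 24.1% | 37.3% | 77.9% |
| 10% | 100% | 29.1% | 42.3% | 74.7% |

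**The case against.** The strongest reply is that section 4.1 names no visit and is written in the present tense, so a site could apply both criteria on the day of randomisation. The project EDD gives gestational age on any later date without a new test, so a single mark in Table 2 does not prove that the limit is ignored at Visit B. One exclusion, known major fetal malformation (4.2), is carried expressly to randomisation. All of this is fair: the protocol nowhere says that screening values suffice. But sections 4.3 and 6.2 tie the decision to screening, and neither section 5.3 nor 6.3 asks for confirmation. The malformation exclusion shows that the protocol anchors a criterion to randomisation when it means to.

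It can also be said that a nominal one-week gap makes large overruns uncommon, that the criterion aims to raise a likelihood and guarantees nothing, and that extended visit windows and home visits (6.12) reduce missed assessments. These points limit the size. They do not remove the conflict with the 30-day rule.

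Several stronger readings are tempting but unsupported:

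- **That smoking is not re-checked.** It is measured at Visit B; what is missing is a rule that uses the result.
- **That late starters will deliver before completing treatment.** Only some may.
- **That third-trimester exposure comes from the gap.** Even with the limit held at Visit B, dosing would run to 36w0d-36w6d.
- **That the treatment comparison is biased.** The gap precedes randomisation and affects both arms alike. Section 7.2.2 also lists baseline gestational age and daily smoking rate as possible covariates.

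**Conclusion.** The point holds for gestational age. As written, the plan permits a first dose at 30w3d-31w2d and a last scheduled dosing day at 40w2d-41w1d, which conflicts with the reason section 4.1 gives for the limit. This follows from the protocol's own dates and needs no assumption beyond how 26 weeks is read. A flat statement that women can be randomised at 31 weeks would need the 26w6d reading; under 26w0d the maximum at Visit B is 30w2d.

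How many women are affected cannot be known from the documents. The figures of about 16% and 7% rest on an assumed uniform screening age, the 26w6d reading and the stated gap patterns; they are illustrations.

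The smoking half is secondary. If 3% to 10% had quit before randomisation and half to all of them stayed quit, power would fall from about 87% to about 85-84% at 3% and 78-75% at 10%. Of the scenarios shown, only the 10% ones fall below 80%. The documents give no pre-randomisation quit rate and no basis for assuming that nobody relapses.

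**What to change.** Reconcile sections 4.1, 6.2, 6.3 and 6.12. State the visit at which each criterion must be met, and define the gestational limit in days. The limit itself and its reference date are for the sponsor to decide.

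Then add two lines to the randomisation form at Visit B, completed before the form is sent: gestational age that day, calculated from the project EDD, and whether the smoking criterion is met, using the CO and TLFB collected at that visit. Where part of Visit B is done by telephone, section 6.3 already puts the interview before the in-person visit, so the TLFB can be available in time.

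The cost is a short amendment and the form change, with no new test. Some women screened near the limit would have to be booked sooner or would become ineligible, and women who quit between the two visits would not be randomised.

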#### 3.2 Primary Study Endpoints

CONFIDENTIAL

This material is the property of the University of Pennsylvania. Do not disclose or use except as authorized in writing by the study sponsor

- Primary smoking status will be assessed using the Timeline Follow-back method (165) and by using carbon monoxide (CO) concentration to biochemically verify the self-report. Participants will be considered to be abstinent if they self-report abstinence (not even a puff

of a cigarette) for  $\geq 7$  days prior to the assessment after 10 weeks of treatment and at 24 weeks post-TQD and have a CO  $\leq 10$  ppm at that time (166-167). As per convention, participants are assumed to be smoking if they self-report to be smoking at the time point, cannot be reached to provide data at the time point, fail to provide a breath sample at the time point, or provide a breath sample at the time point that has a CO concentration  $> 10$  ppm (166).

- For adverse effects, our primary outcome will be the frequency of moderate or severe side effects from a checklist of bupropion-related side effects (derived from completed bupropion studies), as well as those elicited with open-ended questions, through regular obstetrics visits, and assessments triggered by any pregnancy-related complication. Adverse effects will be systematically assessed by study personnel at 5 time points over the course of the 10-week study and can trigger dose reductions or suspension of medication.
- Birth outcomes obtained from labor and delivery records (permission for which will be included in the informed consent form) will include gestational age, overall and spontaneous preterm birth (i.e., at less than 37 weeks), infant birth weight, whether small for gestational age (i.e.,  $< 10^{\text{th}}$  percentile birth weight for gestational age as determined by the Alexander curve), head circumference, Apgar scores, and NICU admissions. Obstetric complications will include type of delivery and delivery and postpartum complications.

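### A yes at the Visit H reminder call can waive the CO visit on the basis of a different week from the one that defines the week-24 endpoint

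*Combined protocol and SAP*

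**What the plan says.** Section 3.2 defines abstinence as at least 7 days without a puff "prior to the assessment after 10 weeks of treatment and at 24 weeks post-TQD", recorded by Timeline Follow-back (TLFB), with CO of 10 ppm or less at that same time. A woman is assumed to be smoking if, among other reasons, she should "fail to provide a breath sample at the time point". Section 7.2.1 repeats that missing counts as smoking, and section 7.2.2 names week 24 as one of two primary outcome variables.

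Section 6.12 sets the timing of the call: "During the week prior to each of the visits (B through J), a reminder call will be made to the participant". At the Visit H call, "the participant will be asked whether she had smoked at all during the previous week". Two branches follow. After a yes: "If she acknowledges having smoked, an in-person visit is not required but may be held". After a no: "If she reports no smoking, an in-person visit will be conducted to verify self-report using breath CO measurement". The same section allows a wide window ("Visit H will be held plus or minus 28 days from the scheduled 24 week post-TQD") and asks for CO at other in-person contacts when feasible, naming delivery and the 6-week postpartum visit.

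Section 6.9 and Table 2 place TLFB and CO at Visit H, with CO in person only. Table 3 pays for Visit H by telephone or in person.

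**The concern.** The call asks about the week before the call. The endpoint counts back from the assessment. Because the call precedes the visit by up to a week, a yes can refer to smoking that lies wholly outside the endpoint week, yet it removes the requirement for the breath sample without which a woman cannot be scored abstinent.

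Any error goes in one direction. A no is tested by TLFB and CO at the visit, so smoking after the call can be picked up. A yes need not be tested, so 7 smoke-free days completed after the call can be missed. The women concerned have recently quit or have lapsed and recovered. The plan expects them: lapse and recovery events are a secondary outcome (3.3), and the postpartum boosters help relapsed women set a new quit date (6.10). At stake is the accuracy of the week-24 quit rates, and a little power.

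**Working it through.** **1. The two windows.** Take the planned Visit H as day 0 and count whole days back. The endpoint week (3.2) is days −7 to −1. A call on day −k, with k = 1 to 7 (6.12), asks about days −(k+7) to −(k+1).

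- Days shared by the two weeks: 7 − k.
- Days asked about that lie before the endpoint week: −(k+7) to −8, which is k days.
- Smoke-free days needed on the visit date to have answered no truthfully and stayed abstinent: 7 + k.

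| k | Days asked about | Shared with endpoint week | Smoke-free days needed |
|---|---|---|---|
| 1 | −8 to −2 | 6 | 8 |
| 4 | −11 to −5 | 3 | 11 |
| 7 | −14 to −8 | 0 | 14 |

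If calls were spread evenly over k = 1 to 7 (an assumption), the mean k is 28/7 = 4 days.

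**2. The scoring path.** Take a call at k = 4 and a last cigarette on day −9. She answers yes truthfully. On day 0 she has been without a puff on days −8 to −1, so she meets the 7-day criterion. If the optional visit is not held and no other CO is used, 3.2 scores her as smoking. A telephone TLFB does not change this, because it yields no breath sample.

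**3. The plan's own power figure.** The documents give no figure for the waiver itself, so the stated week-10 power serves as the check on method. Inputs (7.1, 7.1.1 and 5.3): 21.2% against 35.9%, n = 180 per arm, two-sided α = 0.05.

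Power = Φ{[(p₂ − p₁) − 1.96·√(2p̄(1 − p̄)/n)] / √[(p₁(1 − p₁) + p₂(1 − p₂))/n]}

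With p̄ = 0.2855: (0.147 − 1.96 × 0.0476)/0.0470 = 1.143, so power is 87.3%. With unpooled variance it is 87.9%, and with a Wald test on the log odds ratio 86.4%. The stated 88% is reproduced. The rates give an odds ratio of 2.08, stated as 2.1.

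**4. What lost abstainers would cost at week 24.** Section 7.1.1 gives no week-24 rates. It says the odds ratio is similar and then states 80% power. I assume an odds ratio of 2.1 and that the 80% refers to week 24, and solve for the placebo rate: 14.8% against 26.8%, or about 0.148 × 180 = 27 and 0.268 × 180 = 48 abstainers. Let m be the share of true abstainers lost, equal in both arms, so each rate is multiplied by (1 − m).

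| m (assumed) | Risk difference, points | Odds ratio | Power |
|---|---|---|---|
| 0 | 11.95 | 2.10 | 80.0% |
| 2% | 11.71 | 2.09 | 79.0% |
| 5% | 11.35 | 2.08 | 77.4% |
| 10% | 10.75 | 2.06 | 74.6% |

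At m = 10% the women lost are about 0.10 × 27 = 2.7 on placebo and 0.10 × 48 = 4.8 on bupropion. With the week-10 rates instead, power goes from 87.3% to 86.4%, 84.9% and 82.2% at the same three values of m. The true m is not in the documents.

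**The case against.** The strongest case against has three parts.

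First, a reader might infer that these women are always scored as smokers on the wrong week. The documents do not say that. The visit is optional after a yes, not cancelled. CO is sought at other contacts, and Visit H was given its wide window so that it could coincide with them. Nothing says that a later in-window CO is disregarded. Moreover, if no visit is held there is no visit week to compare with: the call can itself fall inside the ±28 days, and on that reading a yes about the previous week is a valid 7-day answer. This stands as a limit on the wording: such women can be miscoded. It does not remove the problem. The endpoint is recorded by TLFB, which section 6.9 places at the visit, and the call is described as a reminder of that visit. If the call did count as the assessment, women answering yes and no would be assessed on different dates by different means. The plan states neither which date is the week-24 assessment when the visit is waived nor whether a later CO overrides a yes.

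Second, a reader might infer that the bupropion effect is understated because more recovering women are lost on the active arm. The documents do not support this. Staff and participants are blinded (5.7), and boosters go to both arms. Dosing ends at Week 10, which is 9 weeks after the Week 1 quit date, so Visit H is nominally 24 − 9 = 15 weeks later (11 weeks at the early edge of the window). Similar loss in both arms is the safer expectation.

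Third, a reader might put the affected group at, say, 2–5% of all randomised women (0.02 × 180 = 3.6 to 0.05 × 180 = 9 per arm). Spread over the mean 4-day stretch, that is 0.5–1.25% per day. Held constant over 24 × 7 = 168 days, it implies 0.84–2.1 new quits of at least 7 days per woman. No passage supports such a rate, and the guess also supposes that no optional visit is ever held.

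**Conclusion.** The point holds in limited form. A stated procedure in 6.12 conflicts with a primary endpoint definition in 3.2: where the optional visit is not held, a woman can need 8 to 14 smoke-free days instead of 7, and only no answers must be verified. This takes the planned Visit H as the anchor for the endpoint week, which sections 3.2 and 6.9 suggest but do not state outright.

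The number affected cannot be derived and is probably small, since it needs a last cigarette within one particular stretch of 1 to 7 days and no later CO. With similar loss in both arms, the week-24 quit rates and risk difference fall in proportion to m, while the odds ratio barely moves. Power would fall by 1.0 point at m = 2% and 5.4 points at m = 10%, under the assumed week-24 rates. This is a cheap improvement. It does not threaten the trial's conclusion, and it is no evidence of bias between arms.

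**What to change.** Amend 6.12 as follows.

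- Use the Visit H reminder call for scheduling only.
- After a yes, complete the Visit H TLFB; telephone is acceptable and Table 3 already pays for it. Waive the in-person visit only if that TLFB shows smoking in the 7 days before it.
- Otherwise require an in-person visit within the existing ±28 days. Repeat the TLFB and take CO on that same date, and treat that date as the week-24 assessment. The same-day rule matters: 3.2 wants CO at the time of the self-report, so a telephone TLFB followed by CO days or weeks later would create a new mismatch.

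The cost is a wording change and a few additional in-person visits, each adding $15 in travel under Table 3 ($60 against $45). For these women the assessment may fall somewhat later, but inside a window the plan already accepts.
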